The study was conceived and initiated by professor [name], Department of Gastroenterology & Hepatology, Aalborg University Hospital. It is economically supported from Steno Diabetes Centre North Denmark who will provide equipment and personal for continues glucose monitoring (CGM). Various funds will be applied for, to cover any additional financial expenses. Potential grants from other funds are deposited in a project account at Aalborg University Hospital, which principal investigator [name] is responsible for. The involved researchers conduct the trial of general scientific interest without personal financial gain. All data will be publicly available after publication based on reasonable request.

4. Roles and responsibilities

The present studies will be conducted in compliance with this protocol, the guidelines of the World Medical Association Declaration of Helsinki in its revised edition (Fortaleza, Brazil, October 2013) and designated Standard Operating Procedures. The project will be conducted in collaboration between researchers from Centre for Pancreatic Diseases at Aalborg University Hospital and Steno Diabetes Centre North Denmark. The researchers have clinical and health technology backgrounds and a long track record on research into diabetes, pancreatic diseases, and epidemiology as well as major experience with leadership of clinical and epidemiological studies. The principal investigator [name] is clinical professor in pancreatology at Aalborg University and chief physician at Aalborg University Hospital where he is the leader of Centre for Pancreatic Diseases. He has a long track record of clinical and epidemiological projects within acute and chronic pancreatitis and has a special interest in metabolic complications of pancreatic diseases. The co-investigator [name] is a senior researcher at Steno Diabetes Centre North Denmark and associate professor at Aalborg university. He has a proven track record of epidemiologic and health technology studies within type 2 diabetes and a special interest in CGM and management of hypoglycaemia. Staff at Steno Diabetes Centre North Denmark and Mech-Sense, Department of Gastroenterology and Hepatology will be employed to oversee the studies. For sub study 3, associate professors [name], [name] and [name] from Hvidovre University Hospital and Odense University Hospital will participate. They all have extensive experience with clinical management and research in pancreatic diseases. Professors [name] and [name] will provide assistance with analysis and interpretation of results from the arginine test and analysis of intestinal/pancreatic hormones. Professors [name] and [name] are international leading experts in endocrinology and gastroenterology with extensive experience in research management and will serve as consultants on the project.

5. Time schedule

The project is expected to be initiated (first subject included) in April 2022 and concluded (last subject, last visit) by March 2023. An overview is given in the diagram below.

	2021		2022				2023				2024	
	Q3	Q4	Q1	Q2	Q3	Q4	Q1	Q2	Q3	Q4	Q1	Q2
Writing of protocol												
Regulatory affairs												
Conduct of studies												
Data analysis												
Writing and submitting articles												

6. Purpose and scientific background

6.1 Introduction and purpose

Post-pancreatitis diabetes mellitus (PPDM) is a frequent complication of chronic pancreatitis and occurs in up to 80% of patients during their disease course^{1,2}. PPDM prognosis and management has not been widely studied as patients with PPDM are typically excluded from observational studies and randomized controlled trials of glucose lowering therapies. Therefore, prognosis and management strategies have mostly been extrapolated from other diabetes subtypes. Furthermore, patients with PPDM are frequently misdiagnosed and treated as type 2 diabetes^{3,4}. This is problematic as PPDM has a distinct pathophysiology and clinical presentation. Hence, patients with PPDM often have “brittle diabetes” characterized by fluctuating blood glucose levels, frequent hypoglycaemic episodes, and poor glycaemic control^{1,5}. However, there is a lack of systematic investigations of glucose homeostasis in relation to PPDM.

The use of continuous glucose monitoring (CGM) improves glycaemic control and risk of hypoglycaemia compared to self-monitoring of blood glucose (SMBG) in people with type 1 and insulin-treated type II diabetes⁶⁻⁹. However, the effect of CGM on hypoglycaemic risk has never been investigated in PPDM patients.

The overall purpose of this project is to study glucose variability and hypoglycaemia in patients with PPDM. The project is organized into three sub studies aiming to: 1) Investigate short-term glucose variability assessed by continuous glucose monitoring (CGM) and the effect of CGM on hypoglycaemia compared to SMBG, 2) investigate long-term glucose variability based on visit-to-visit haemoglobin A1c (HbA1c), and 3) investigate the prevalence of, risk factors for and awareness

of hypoglycaemia using standardized patient-reported outcomes. Patients with type 2 diabetes are included as the most clinically relevant comparison group⁵. The project will provide novel information on glucose variability and prevalence of hypoglycaemia among patients with PPDM using the most updated classifications and technologies. This information can be used to inform prognosis and identify relevant targets for optimization of management.

6.2 Scientific background and literature review

6.2.1 Pathophysiology of post-pancreatitis diabetes mellitus

Chronic pancreatitis is characterized by a fibro-inflammatory process that leads to islet cell injury with ensuing beta-cell loss and decreased insulin secretion^{1,10}. This has for long been considered the primary mechanism of PPDM. However, injury to pancreatic islets also results in impaired secretion of pancreatic polypeptide resulting in hepatic insulin resistance and increased hepatic glucose production¹¹. Likewise, impaired secretion of glucagon and somatostatin compromise glucose counter regulation during hypoglycaemia which may be an important mechanism for the frequent hypoglycaemic episodes observed in these patients¹². The majority of patients with PPDM also have pancreatic exocrine insufficiency and malassimilation of intestinal nutrients, which has been associated with a blunted incretin response during oral feeding that are only partly reversed by pancreatic enzyme replacement therapy^{1,13,14}. In addition, abdominal pain and other complications related to chronic pancreatitis may compromise nutritional intake and lead to malnutrition and depleted glycogen stores which again compromise gluconeogenesis during fasting¹⁵. Finally, type 2 diabetes related risk factors may also be implicated in the pathogenesis of PPDM². The combined effects of these mechanisms are believed to result in greatly fluctuating blood glucose levels and excess risk of hypoglycaemia i.e., a “brittle diabetic state” - **figure 1**^{2,16}.

[figure not shown]

Figure 1. Pathophysiological mechanisms associated with the “brittleness” in PPDM. PP, pancreatic polypeptide; EPI, exocrine pancreatic insufficiency; CP, chronic pancreatitis; PPDM, post-pancreatitis diabetes mellitus

Notwithstanding the improved understanding of PPDM pathophysiology, most past observations of glucose homeostasis in PPDM patients come from small studies in poorly defined patient groups and have mostly been based on outdated definitions and technologies¹. Also, the problem of “brittle diabetes” in relation to PPDM has not been investigated in the era of modern glucose lowering medications such as long-acting and ultra-long-acting insulin analogues that may reduce risk of hypoglycaemia.

6.2.2 Continuous glucose monitoring

SMBG using a glucometer and a capillary blood sample drawn via finger-pricking is used by most people with diabetes. However, this technique has some disadvantages as it is user-dependent and does not capture nocturnal and asymptomatic hypoglycaemia. Also, SMBG cannot be used to predict impending hypoglycaemia as it is based on single-instant blood glucose readings. These limitations can be overcome by using CGM⁶. A CGM system is based on a subcutaneous sensor that automatically measures an individual’s interstitial glucose levels continuously. Based on trends in glucose levels, CGM can predict impending hypoglycaemia and detect fluctuations in blood glucose levels^{17,18}. In people with type 1 diabetes and those with type 2 diabetes on multiple daily insulin injections, CGM improves glycaemic control and reduces time in hypoglycaemia compared to SMBG⁶⁻⁹. It is likely that this effect is also present in patients with pancreatogenic diabetes, but this has never been investigated.

6.2.3 Characterization of glucose variability and association with hypoglycaemia risk

Variability of glucose homeostasis has been increasingly recognized as an important determinant of diabetes-related complications and adverse clinical outcomes beyond HbA1c levels¹⁹. It encompasses two categories of dysglycaemia: i) short-term daily glucose fluctuations that can be assessed by CGM and ii) long-term weekly, monthly or quarterly changes in glucose variability that have typically been assessed by changes in visit-to-visit HbA1c levels. Although the evidence for the relationship between glucose variability and adverse clinical outcomes is not fully clarified at this point, evidence supports a strong association between hypoglycaemic events and both short and long-term glucose variability¹⁹. To the best of our knowledge short and long-term glucose variability and prevalence of hypoglycaemia has not previously been investigated in the context of PPDM using modern technologies and definitions.

6.3 Hypotheses

- **Sub study 1:** Short-term glucose variability and time in hypoglycaemia, as determined by CGM, is increased in patients with PPDM compared to a matched group of individuals with type 2 diabetes; the use of CGM will lead to decreased time in hypoglycaemia compared to SMBG in PPDM patients.
- **Sub study 2:** Long-term glucose variability, as determined by visit-to-visit HbA1c, is increased in patients with PPDM compared to a matched group of individuals with type 2 diabetes.
- **Sub study 3:** Patients with PPDM report high frequencies of self-reported hypoglycaemic events and targetable risk factors for hypoglycaemia can be identified.

7. Methods I: design, setting, participants, and outcomes

7.1 Study designs

- **Sub study 1** is a prospective open-label crossover randomized controlled study of the effect of CGM on hypoglycaemia compared to SMBG in PPDM patients
- **Sub study 2** is a retrospective cohort study of long-term glucose variability, as determined by visit-to-visit HbA1c levels, in PPDM patients compared to matched individuals with type 2 diabetes
- **Sub study 3** is a multicentre cross-sectional study based on patient-reported outcomes (PROs)

7.2 Study settings

Sub studies 1 and 2 will be conducted at Centre for Pancreatic Diseases at Aalborg University Hospital and Steno Diabetes Centre North Denmark. These centres have comprehensive experience in diagnosing, treating, and conducting research on patients with pancreatitis and diabetes. Patients with PPDM will primarily be identified and included via the outpatient clinic at Centre for Pancreatic Diseases but may also be identified after admission with chronic pancreatitis as described in section 7.9 or in the diabetes outpatient clinic. For sub study 2 data are retrieved from Diabetesdatabasen in the North Denmark Region. Sub study 3 is a multicentre study that in addition to the above-mentioned sites also includes pancreas outpatient clinics at Hvidovre University Hospital and Odense University Hospital.

7.3 Eligibility criteria

7.3.1 Inclusion criteria PPDM patients

- Signed informed consent before any study specific procedures*
- Able to read and understand Danish
- Male or female age $\geq 18 \leq 80$ years
- A definitive diagnosis of chronic pancreatitis based on the M-ANNHEIM criteria²⁰
- A diagnosis of insulin treated PPDM based on the World Health Organization criteria for diabetes (HbA1c $\geq 6.5\%$ (48 mmol/mol) and/or fasting plasma glucose ≥ 126 mg/dl (7.0 mmol/l) > 3 months after diagnosis of pancreatitis

*a signed informed consent is waived for patients in sub study 2 which is a register-based study based on data from Diabetesdatabasen in the North Denmark Region.

7.3.2 Exclusion criteria PPDM patients

- Known or suspected abdominal cancer (incl. intestine, pancreas, and the hepato-biliary system)
- Severe pre-existing comorbidities (assessed by investigator upon inclusion)
- Attack of acute or chronic pancreatitis requiring admission within four weeks prior to inclusion
- Use of glucocorticoid medications within four weeks prior to inclusion
- Presence of autoimmune antibodies suggestive of type 1 diabetes
- Prior pancreatic surgery (including total pancreatectomy, pancreaticoduodenectomy, distal pancreatectomy, pancreaticojejunostomy, enucleation, or Frey procedure)
- Prior gastric surgery or vagotomy
- Autoimmune pancreatitis

7.3.3 Comparator groups for sub studies 1 and 3 (individuals with type 2 diabetes)

- Individuals with type 2 diabetes enrolled in the DiaMonT study are included as comparator group in sub studies 1 and 3. Individuals participating in the DiaMonT study undergo CGM for up to three months and provide information on experience with hypoglycaemia and awareness. These data will be used for comparison with the data collected in sub studies 1 and 3. The DiaMonT study is already approved by relevant regulatory bodies (N-20200068) and participants have provided written informed consent upon inclusion and agreed that the collected data can be used for research purposes.
- Individuals with type 2 diabetes are matched to PPDM patients based on HbA1c levels and other relevant parameters including regimens of glucose lowering therapy.
- The following data from the DiaMonT study will be used:
 - Basic demographic and clinical characteristics
 - Information on glucose lowering therapies and other medications
 - Routine biochemical parameters including Hb1Ac
 - CGM metrics
 - Information on hypoglycaemia and hypoglycaemia awareness

Patients from the DiaMonT study will not provide any biological material for this project. Data will be used in compliance with the rules on protection of personal data from the Danish Data Protection Agency.

7.3.4 Comparator group for sub study 2 (individuals with type 2 diabetes)

- Individuals with type 2 diabetes enrolled in Diabetesdatabasen are included as comparator group in sub study 2. Diabetesdatabasen is a health registry maintained by the Business Intelligence Unit in the North Denmark Region and collect anonymised data on individuals with diabetes in the North Denmark Region. In agreement with Danish legislation use of anonymised data from Health Registries do not require informed consent from involved individuals.
- Individuals with type 2 diabetes are matched to PPDM patients based on HbA1c levels and other relevant parameters including regimens of glucose lowering therapy

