7.8 Sample size considerations

- **Sub study 1:** The sample size calculation is based on the primary endpoint described for sub study 1 (time in level 2 hypoglycaemia). A sample size of 24 patients is determined to have at least 80% power to detect a reduction in the percentage of time spent with a glucose value <3.0 mmol/l (level 2 hypoglycaemia), assuming a relative treatment reduction of 50% from a percentage of time spent with glucose value <3.0 mmol/l of 3%, standard error of 2.5%, and type I error rate (2 sided) of 5%. To account for approximately 25% dropouts, the final sample size is set to 30 patients. As there are currently no adequate data on CGM in patients with pancreatogenic diabetes to inform sample size calculations, assumptions are based on findings in older adults with long-standing type 1 diabetes who have an increased risk of hypoglycaemia⁷.
- **Sub study 2:** This is a retrospective cohort study based on data already collected in Diabetesdatabasen and the sample size will therefore be dictated by the number of individuals in the

database. Previous population-based studies from our group have shown that the proportion of patients with PPDM among patients clinically diagnosed type 1 or type 2 diabetes is approximately 1.5%^{4,22}. In Diabetesdatabasen there are currently >5000 unique adult individuals registered, and thus we expect to identify at least 75 PPDM cases which should provide sufficient statistical power to the planned analyses according to a previous study from our group²².

- **Sub study 3:** This is a cross-sectional survey. No previous studies have evaluated the prevalence of self-reported severe hypoglycaemia and related risk factors in patients with PPDM. However, according to recent population-based registry data from our group, patients with PPDM have a risk of hospitalization for hypoglycaemia comparable to that observed for individuals with type 1 diabetes (*unpublished data*). In type 1 diabetes, the yearly prevalence of self-reported severe hypoglycaemia range between 10–53%²³. Thus, we consider a sample size of 200 patients will provide sufficient power to obtain prevalence estimates with reasonable precision and allow for multivariate modelling of putative risk factors associated with severe hypoglycaemia.

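### Sub study 2 applies exclusions to the PPDM group but none to the type 2 comparators, not even for a history of pancreatitis; any bias is probably towards no difference and of unknown size

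*Protocol*

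**What the plan says.** The PPDM side is restricted in two steps. Section 7.3.1 requires definitive chronic pancreatitis and insulin-treated diabetes. Section 7.3.2, headed "7.3.2 Exclusion criteria PPDM patients", then removes eight categories. Some are not specific to pancreatic disease, for example "Use of glucocorticoid medications within four weeks prior to inclusion", "Presence of autoimmune antibodies suggestive of type 1 diabetes", "Prior gastric surgery or vagotomy", abdominal cancer and severe comorbidity. Others are specific to it: prior pancreatic surgery, autoimmune pancreatitis and a recent attack of pancreatitis. The footnote to 7.3.1 exempts sub study 2 from signed consent and from nothing else, so the remaining criteria formally apply to its PPDM cases.

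On the comparator side, section 7.3.4 says "Individuals with type 2 diabetes enrolled in Diabetesdatabasen are included as comparator group in sub study 2" and "Individuals with type 2 diabetes are matched to PPDM patients based on HbA1c levels and other relevant parameters including regimens of glucose lowering therapy". It lists no exclusion.

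Two statements elsewhere bear on this. Section 6.1 says that "patients with PPDM are frequently misdiagnosed and treated as type 2 diabetes". Section 7.8 says that "the proportion of patients with PPDM among patients clinically diagnosed type 1 or type 2 diabetes is approximately 1.5" per cent, and uses that share to predict the number of cases.

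**The concern.** The two groups are selected by different rules, and the difference touches the outcome. Glucocorticoids, cancer, serious comorbidity and type 1 autoimmunity can all plausibly make HbA1c less stable. If such people are removed from the PPDM group but left among the comparators, part of the contrast reflects selection and not type of diabetes.

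The second route is misclassification. Someone coded as type 2 whose diabetes followed acute pancreatitis only, or who has had a pancreatic resection, fails the PPDM criteria but meets everything 7.3.4 asks of a comparator. Matching on treatment regimen to insulin-treated cases plausibly concentrates such people among the comparators.

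The hypothesis in section 6.3 is that variability is higher in PPDM, so both routes would tend to shrink the primary VIM difference and the secondary CV and average real variability differences. Who may enter a comparison group is a matter of eligibility, which section 7.3 sets out to fix.

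**Working it through.** **The plan's own figure.** Section 7.8 gives more than 5000 registered adults and a PPDM share of about 1.5%. 5000 × 0.015 = 75, which reproduces the stated minimum of 75 cases. No VIM difference, SD, alpha, power or matching ratio is given for sub study 2.

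**Dilution by pancreatic diabetes among the comparators.** Let c be the share of comparators whose variability is at PPDM level. The comparator mean moves a fraction c of the way towards the PPDM mean, so:

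- observed difference = (1 − c) × true difference
- sample size needed rises by 1/(1 − c)²

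For power, I assume 75 per group, 1:1 matching, two-sided 5% and 80% power without contamination. The standardised difference is then (1.960 + 0.842) × √(2/75) = 0.457.

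| c | Difference kept | Sample size factor | Power |
|---|---|---|---|
| 0 | 100% | 1.000 | 80.0% |
| 0.75% | 99.25% | 1.015 | 79.4% |
| 1.5% | 98.5% | 1.031 | 78.8% |
| 3% | 97% | 1.063 | 77.6% |
| 5% | 95% | 1.108 | 75.9% |
| 10% | 90% | 1.235 | 71.3% |
| 20% | 80% | 1.562 | 61.1% |

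**Which c is plausible?**

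- *No PPDM removed from the comparators:* c = 1.5%, the protocol's own share.
- *Only cases that fail the PPDM criteria fall back* (assumed 25% to 50% of the 75): 18.75/(4925 + 18.75) = 0.4% and 37.5/(4925 + 37.5) = 0.8%.
- *Comparators confined to insulin users by matching* (assumed 15% to 40% of the other 4925, with all fallback cases on insulin): the lowest value is 18.75/(18.75 + 0.40 × 4925) = 0.9% and the highest is 37.5/(37.5 + 0.15 × 4925) = 4.8%. Power is then about 79% to 76%.

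**The other one-sided exclusions.** Let f be the share of comparators, and g the share of PPDM patients, with a condition that doubles variability. A true PPDM to type 2 ratio R is then observed as R × (1 + g)/(1 + f). The protocol gives neither f nor g, and the doubling is itself an assumption. If g = f there is no distortion. No figure can be derived for this part.

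**The case against.** The strongest reply is that the PPDM group may not be restricted in practice. The glucocorticoid and pancreatitis-attack exclusions look back only four weeks, whereas the endpoint uses up to 48 months of HbA1c. Severe comorbidity is to be judged by an investigator at inclusion, which has no clear meaning in an anonymised register. Section 8.1.4 collects autoantibodies for sub studies 1 and 3, and neither they nor glucocorticoids appear among the items in 8.1.6. If these criteria cannot be applied, much of the asymmetry disappears. This stands as a limit on the size. It does not remove the point, because the protocol then sets criteria for sub study 2 that it cannot carry out and does not say which ones hold.

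The 1.5% is also the share the study expects to identify as cases, and identified cases leave the type 2 pool. That is right, and it is why the fallback scenarios are lower before insulin matching. However, the figure counts PPDM only; a pancreatitis history outside that definition is not quantified.

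Section 8.1.6 registers the Charlson index, section 8.3.1 allows regression adjustment, and 7.3.4 matches on further unnamed parameters. These may help with comorbidity. None of them keeps misclassified pancreatic diabetes out of the comparators. Exclusions that define a chronic pancreatitis population also need no mirror image in type 2 diabetes, which is accepted.

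Finally, a bias towards no difference works against the hypothesis and would not create a false positive. That limits the harm, but a diluted estimate would still understate the contrast the sub study is meant to measure.

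**Conclusion.** The point holds in a limited form. The asymmetry is plain in sections 7.3.1, 7.3.2 and 7.3.4, and section 6.1 gives the reason a pancreatitis exclusion is needed among the comparators. Any bias in the three variability contrasts is probably towards no difference.

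A reader might go further and infer that a large part of the PPDM excess is lost. The documents do not support that. It would need assumed shares of unstable comparators, an assumed increase in their variability, and no such patients in the PPDM group; the four-week and investigator-judged criteria cannot guarantee the last of these over 48 months.

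What can be sized is the pancreatitis part. It takes about 1.5% of the difference at the protocol's own share, and up to about 5% under the assumed insulin matching, with power falling from an assumed 80% to about 76%. This rests on misclassified comparators having PPDM-level variability. A material loss would need contamination nearer 10% to 20%, for which the protocol gives no support. The effect of the remaining exclusions is unknown.

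**What to change.** In section 7.3.4, exclude comparators with any recorded acute or chronic pancreatitis, pancreatic surgery or pancreatic cancer. Finding the PPDM cases already requires pancreatitis status, and section 8.1.6 lists pancreatitis details and surgical history among the items to be obtained.

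For the 7.3.2 exclusions that are not specific to pancreatic disease, state which can be read from Diabetesdatabasen. Apply those equally to both groups, and apply the unreadable ones to neither group in sub study 2.

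For the DiaMonT comparators in section 7.3.3, apply the pancreatitis exclusion only if that history is recorded there; that study's own eligibility criteria are not shown.

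The cost is eligibility wording and a register filter, set before the matched data are analysed so that the change is not post hoc. Some comparators are lost. The available pool is smaller than the figure of more than 5000, which counts all registered adults with diabetes, and matching reduces it further. The number remaining after the filter should be checked.

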7.6 Outcomes

7.6.1 Primary endpoints

- **Sub study 1:** Difference (monitoring with CGM vs. SMBG) in time spent with glucose value <3.0 mmol/L (level 2 hypoglycaemia) during the last two weeks of each study period
- **Sub study 2:** Long-term glucose variability (up to 48 months) expressed as difference in visit-to-visit HbA1C VIM (Variability Independent of the Mean) between PPDM patients and individuals with type 2 diabetes patients
- **Sub study 3:** Proportions of patients with severe hypoglycaemia during the preceding 12 months. Hypoglycaemic endpoints are defined according to the latest ADA recommendations²¹

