7.6.2 Secondary endpoints

Sub study 1:

- Short term (20 days) difference in CGM metrics between PPDM patients and individuals with type 2 diabetes
- CGM time in range (glucose value >3.9 mmol/L and ≤10 mmol/L)
- CGM time below range (glucose value ≤3.9 mmol/L)
- CGM time above range (glucose value >10 mmol/L)
- CGM metrics of glucose variability (SD (Standard deviation) and CV (Coefficient of Variance) of mean glucose, mean amplitude of glycaemic excursions [MAGE] and continuous overall net glycaemic action [CONGA])

Sub study 2:

- Difference in HbA1C CV between PPDM and type 2 diabetes patients during up to 48 months follow-up
- Difference in HbA1C average real variability between PPDM and type 2 diabetes patients during up to 48 months follow-up
- Difference in HbA1C level trajectories between PPDM and type 2 diabetes patients during up to 48 months follow-up

Sub study 3:

- Risk factors for hypoglycaemia including demographics and routine clinical and biochemical parameters
- Awareness of hypoglycaemia based on the Clarke hypoglycaemia awareness survey
- Proportions of patients with ketoacidosis during the preceding 12 months

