8.3 Plan for statistical analyses

8.3.1 Statistical methods

- **Sub study 1:** CGM metrics collected in periods with monitoring using CGM vs. SMBG are compared using multiple linear regression models. Further, regression models are fitted to investigate associations between baseline characteristics and measures of glucose variability.
- **Sub study 2:** HbA1c variability metrics are compared between PPDM and type 2 diabetes patients using multiple linear regression models. Hb1Ac level trajectories are visually characterized and latent class analysis is used to define distinct patient clusters.
- **Sub study 3:** Prevalence estimates of hypoglycaemia are reported as point prevalence estimates with 95% confidence intervals. Logistic and Poisson regression models are fitted to investigate associations between patient characteristics and hypoglycaemia risk.

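### Sub study 2 matches type 2 controls on HbA1c and then compares HbA1c trajectories, so the level part of that secondary comparison is largely set by the matching

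*Protocol*

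**What the plan says.** Sub study 2 is a retrospective cohort from a regional diabetes register. Protocol section 7.3.4 states that its type 2 comparators are "matched to PPDM patients based on HbA1c levels and other relevant parameters", and names the glucose-lowering regimen as one of those parameters. It does not say which HbA1c is meant (an index value, an earlier value or a mean over follow-up), nor within what window or tolerance.

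The primary endpoint in section 7.6.1 is HbA1c VIM, a variability metric built not to depend on the mean. Section 7.6.2 adds three secondary endpoints: HbA1c CV, HbA1c average real variability, and "Difference in HbA1C level trajectories between PPDM and type 2 diabetes patients during up to 48 months follow-up".

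Section 8.3.1 plans multiple linear regression for the variability metrics. For the third secondary endpoint it says that "level trajectories are visually characterized and latent class analysis is used to define distinct patient clusters". The hypothesis in section 6.3 concerns variability only: "Long-term glucose variability, as determined by visit-to-visit HbA1c, is increased in patients with PPDM compared to a matched group".

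**The concern.** For VIM, CV and average real variability, similar HbA1c levels in the two groups are a sensible control. For the trajectory endpoint, HbA1c level is the quantity being compared. Choosing controls because their HbA1c agrees with that of the PPDM patients makes the groups alike on that outcome before any analysis.

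Two misreadings could follow. A real difference in level could be reported as small or absent. And if the courses are in truth parallel, controls picked for an unusual baseline value drift back towards their own mean, so the curves start together and then separate. A visual reading could take that separation for a difference in disease course. Latent classes that differ by level would be affected too, because the matching changes how many controls fall into the high classes.

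**Working it through.** **The plan's own figure.** Section 7.8 expects at least 75 PPDM cases, from more than 5000 registered adults and a PPDM share "among patients clinically diagnosed type 1 or type 2 diabetes is approximately 1.5" per cent: 5000 × 0.015 = 75. This reproduces. No power statement rests on the trajectory endpoint.

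**Assumed inputs (not in the documents).** HbA1c SD 15 mmol/mol; within-person correlation r = 0.5, 0.7 or 0.9, constant over time; a constant level gap G = 5 mmol/mol or none; a slope difference of 0 or 2 mmol/mol per year; visits every 6 months from 0 to 48 months (nine values). The simulation used 4,000 PPDM patients and 120,000 potential controls with nearest-neighbour matching.

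**Formula for matching on one baseline value.** Let the PPDM mean be m + G and the type 2 mean be m. A control with baseline value y has expected later value m + r(y − m). Over the PPDM patients, y averages m + G, so matched controls later average m + rG, while the PPDM patients still average m + G. The later gap is G − rG = (1 − r) × G. The fraction removed is r, whatever G is.

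**Result with G = 5 and parallel true courses (true slope difference 0):**

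| r | Gap at matching | Later gap, formula | Later gap, simulated | Share removed, simulated | Slope per year, matching visit included | Slope per year, excluded |
|---|---|---|---|---|---|---|
| 0.5 | 0 | 0.5 × 5 = 2.5 | 2.68 | 1 − 2.68/5 = 46% | 0.37 | 0.02 |
| 0.7 | 0 | 0.3 × 5 = 1.5 | 1.77 | 1 − 1.77/5 = 65% | 0.26 | 0.03 |
| 0.9 | 0 | 0.1 × 5 = 0.5 | 0.60 | 1 − 0.60/5 = 88% | 0.03 | −0.07 |

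Formula and simulation agree to within 0.3 mmol/mol. The slope columns show the false divergence. It comes from the step between the matching visit and the next one, and it goes when the matching value is left out.

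**Matching on the follow-up mean.** The simulated mean gap over all visits is 0.00 at every r, so the whole mean level difference is removed. The starting point is displaced as well. With equal true starting levels and a slope difference of 2 per year, the true gap runs from 0 to 8 and averages 4. Subtracting that average makes PPDM patients appear to start about 4 lower (simulated 3.6 to 4.1 lower).

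**What is kept.** A true slope difference of 2.0 per year came back as 2.03 to 2.37 under baseline matching with all visits, 1.94 to 2.10 without the matching visit when a level gap was also present, and 1.94 to 2.11 under follow-up-mean matching. With equal true starting levels, baseline matching left 4.4 to 4.6 of a true later mean difference of 4.5.

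**Limit of the check.** These slope results assume constant r. If r falls with time, the remaining gap grows. For example, with G = 5, a fall in r from 0.8 to 0.5 moves the gap from 0.2 × 5 = 1.0 to 0.5 × 5 = 2.5. Some false divergence would then persist even with the matching value excluded.

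**The case against.** The strongest reply is that a trajectory is about shape, and shape survives. The protocol plans no test of mean level, and a true slope difference is recovered nearly in full under either matching rule. This stands. A reader might infer that the matching removes most of what the endpoint is meant to show. The documents do not support that, because the loss is confined to the level component. But section 7.6.2 does not define the endpoint as slope or change. It speaks of level trajectories, so level is part of what will be plotted and classified.

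Second, matching on level serves the aim of the sub study. The hypothesis is about variability, and section 6.2.3 presents variability as informative beyond HbA1c level. This also stands. A reader might infer that HbA1c should be dropped from the matching altogether. That would change the comparator for the primary and two secondary endpoints in order to serve a third secondary one, a trade-off that the documents do not call for.

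Third, the choice of HbA1c value, the window and the tolerance may be set in an analysis plan that is not shown. This is fair, and their absence is not the point made here. Whichever value is chosen, a set matched on HbA1c loses part or all of the level difference, and analysis of that set alone cannot bring it back.

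Fourth, a comparison of patients with the same starting HbA1c is a legitimate conditional contrast. That is so, provided it is described as such.

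**Conclusion.** The point holds for the level component of one secondary endpoint. Under baseline matching the gap is 0 at the start and (1 − r) × G later, which removes about 50 to 90% for an assumed r of 0.5 to 0.9 (46 to 88% in simulation). Under follow-up-mean matching the mean gap is removed entirely. Parallel courses can show a false early divergence under baseline matching.

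The protocol gives neither r nor an expected level gap, so the size in mmol/mol is illustrative. The fraction removed depends on r and not on G. Slope differences are largely kept. A reader might also infer that the main result of sub study 2 is compromised. It is not: VIM and the variability hypothesis are unaffected. Severity is minor to moderate.

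**What to change.** Keep the HbA1c-matched comparators for VIM, CV and average real variability. For the trajectory endpoint, draw a second comparator set from the same register, matched on the other parameters (section 7.3.4 names treatment regimen) but not on HbA1c, and state in sections 7.3.4 and 7.6.2 which set serves which endpoint.

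If only the HbA1c-matched set is used, match on one HbA1c value at or before the index date, exclude that value from the outcome series, and interpret the trajectories as change over time only, not as a difference in level. This fallback is weaker: it gives up the level comparison and removes the false divergence fully only if the within-person correlation is stable over time.

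The cost is a second matching run in existing register data and two comparator sets to report and explain. No new data collection is needed.
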